2. INTRODUCTION AND BACKGROUND

2.1 Background Information

Renal transplantation is considered to be the best treatment option for patients with end stage kidney disease in terms of quality of life and survival outcomes, as well as relative cost efficiency compared to dialysis.(1) Transplant recipients are susceptible to wound complications, arguably the most common post-transplant surgical complication, which may contribute to an additional risk of graft rejection or failure, prolonged length of stay, readmission and re-operation, as well as increased treatment costs. (2)

Wound complications have been previously superficial or deep dehiscence and/or infection, perigraft collections or seromas, cellulitis, lymphocoeles, and prolonged wound drainage. Studies have shown that the most important risk factors for wound complications in transplantation are immunosuppression and obesity (3). The incidence of wound infection in the presence of immunosuppression is approximately 7%, and more potent immunosuppressive agents are thought to result in a higher incidence of wound complications. (4) Comparing patients with high (>30) and low BMI (<30) patients, meta-analyses have demonstrated a significantly higher risk of wound infection (RR = 3.13, CI, 2.08–4.71; P <0.001), and wound dehiscence (RR 4.85, CI, 3.25–7.25; P <0.001). (5)(6)

Other relevant factors in renal transplantation include surgical technique and expertise, reoperative procedures, the presence of a haematoma, as well as recipient comorbidities such as advanced age, diabetes, malnutrition, dialysis (haemo- and peritoneal), and prolonged uraemia. The surgical closure technique of the incision, in particular, the precise closure of defects in each layer, has also been identified as an independent factor in reducing wound complications. (7) (8)

Negative pressure wound therapy (NPWT) utilises a foam sponge, in combination with a semipermeable adhesive dressing and a vacuum pump device to increase blood flow, drain fluid and exudate, and contract wound edges. Meta- analyses have suggested that when compared to standard wound dressings on closed incisions, NPWT significantly decreases wound size and healing time, with a significant reduction of risk of surgical site infections (RR=0.54, p= 0.01), and a significant reduction in risk of seroma formation (RR=0.48, p=0.01). (9) (10) (11).

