5.2 Eligibility Criteria

5.2.1 Inclusion Criteria

The participant:

1. is an adult ≥ 18 years old, regardless of comorbidities or BMI
2. is able to provide their own informed consent
3. will undergo open renal transplant surgery, including those who undergo dual renal transplant or simultaneous pancreas transplant.
4. will require a surgical incision(s) likely to be able to be covered completely by one or more Prevena Incision Management Systems.
5. is willing and able to return for the required follow up assessments.
6. if concurrently enrolled in a clinical trial it must not impact on patient health or the surgical incision site and the study must be documented

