5.4 Enrolment and Randomisation Procedures

All patients presenting for a renal transplant over a 24 month period at one of the participating sites will be eligible for enrolment in this study. Patients who sign the Participant Information Sheet and Consent Form (PISCF) and fulfil all inclusion and exclusion criteria, as well as compliance with contraindications listed in the Prevena IFU, will be considered eligible for study participation. Participants may recruited at any point prior to surgery once surgery is confirmed, ideally at the time of admission to hospital for the procedure, or if this is not possible, at the time consent is obtained for the surgery. A unique study identification number is then assigned to enrolled participant by the study investigators.

Participants who signed the PISCF but do not fulfil all inclusion and exclusion criteria, IFU related indications and contraindications, hospital standard of care tests, or who withdraw informed

consent prior to the procedure are screen failures. They will be documented on the screening and enrolment log with the screening failure reason. For the purposes of analysis, an Intention to Treat (ITT) sample will be based on all enrolled subjects, and a secondary as per-protocol analysis will be based on all patients who have the intervention of having a dressing placed on the closed incision following renal transplant.

Patient registration will occur prior to surgery on an online research database (REDCap; Vanderbilt University, Nashville, USA) hosted at Royal North Shore Hospital (19). Randomisation via REDCap will occur when the patient fulfils all intra-operative exclusion criteria and after commencement of skin closure (defined as closure to the muscle, subcutaneous tissue and skin). Randomisation will be stratified by site, with block randomisation by variable block size in a 1:1 ratio. , The surgical team, clinical staff, and patient will not be blinded to the intervention status.

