9 STATISTICAL METHODS

9.1 Sample Size Estimation

Wound infection rate have been estimated between 5 and 30% based on a current literature, including a systematic review and meta-analysis.(3)(10) Weighting the participating site's preliminary audit data by expected enrolment rates, the average wound complication rate was estimated to be 15%. NPWT has been suggested to offer an approximate 46% reduction in wound infection rates for abdominal incisions (3)(10).

Based on a two-sided type one error of $\alpha = 0.05$ and a type two error of $\beta = 0.2$ (corresponding to a power of 80%) a total sample size of 239 patients per group (478 in total) is needed to evaluate primary

endpoints, which was calculated using the power formula for a chi-square test without Yates' continuity correction due to the large sample size and binary dependent variable (22). Accounting for potential loss to follow up, which is estimated to be minimal, as every patient receiving a kidney transplant is planned to follow up every day for 30 days postoperatively, the sample size has been rounded up to 250 per arm (500 total). Missing data from patients who fail to have endpoints recorded will be treated on an intention to treat basis with last observation carried forward.

Estimated mean wound complication rate in control arm across 3 sites : 15%

Site 1 : 5-10% (60 transplants per year, audit data demonstrates 5% dehiscence rate)

Site 2 : 8-15% (90 transplants per year, audit data demonstrates 8% infection rate)

Site 3 : 18-25% (100 transplants per year, audit data demonstrates 18% dehiscence rate)

Conservative estimate of treatment effect: ~50% reduction in all wound complications with closed incision NPWT over lower abdominal/groin wounds (Rutherford Morrison) in high risk population.

Estimated complication rate for Prevena arm (intervention) = 7%

Dichotomous Endpoint, Two Independent Sample Study

Sample Size	
Group 1	239
Group 2	239
Total	478

Study Parameters	
Incidence, group 1	15%
Incidence, group 2	7%
Alpha	0.05
Beta	0.2
Power	0.8

$$N_1 = \left\{ z_{1-\alpha/2} * \sqrt{\bar{p} * \bar{q} * \left(1 + \frac{1}{k}\right)} + z_{1-\beta} * \sqrt{p_1 * q_1 + \left(\frac{p_2 * q_2}{k}\right)} \right\}^2 / \Delta^2$$

$$q_1 = 1 - p_1$$

$$q_2 = 1 - p_2$$

$$\bar{p} = \frac{p_1 + k p_2}{1 + K}$$

$$\bar{q} = 1 - \bar{p}$$

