9.3 Statistical Analysis Plan

Statistical analysis will be pre-specified and conducted according to both principles of intention to treat and per-protocol analysis, using SPSS version 20 (IBM, Armonk, NY, USA). Each incision will be randomized to the Prevena or standard dressing group. In the case that a patient requires bilateral incisions, both incisions will be allocated to the same treatment arm and counted as a single incision. Baseline characteristics of the two groups will be recorded and compared using Student's t-test and chi-square test for continuous and discrete data respectively. The primary outcome, the proportion of wound complications, will be compared between the Prevena and standard dressing groups using a chi-square test without Yates' continuity correction with a two-sided alpha of 0.05 at the final analysis using the Peto approach to preserve the overall significance level of 0.05 (23). An absolute risk increase/reduction for wound complications will be presented for the use of Prevena, as well as the number needed to treat in order to prevent specific wound complications. Patients lost to follow-up will be used in an intention-to-treat analysis with last observation carried forward.

The secondary outcome of identification of risk factors for wound complications will be assessed by multiple logistic regression of collected variables to assess their odds ratio. To prevent overfitting with the selected sample size, variables will be stepwise selected and also assessed for multicollinearity with the significance level of the dependent variables adjusted for multiplicity. Secondary outcomes will be compared between groups using a chi-square or Fisher's test for reoperation rate and delayed graft function and t-test for continuous variables, including the pain scale and quality of life. Non-normally distributed continuous variables will be tested for and compared using the Mann-Whitney *U* test. Survival analysis will be performed for allograft survival time with subjects without events censored at the 90 day final observation. A *p* value of less than 0.05 will be considered significant for the secondary outcomes and all tests will be two-sided.

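### Section 9.3 tests the primary outcome unadjusted, so a BMI effect that the protocol itself calls leading is left out: the test is valid, but precision is lost and a chance imbalance has no pre-specified answer

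*Combined protocol and SAP*

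**What the plan says.** - **Who enters.** Section 5.2.1 sets no BMI limit: it admits adults "regardless of comorbidities or BMI".
- **What the protocol believes about BMI.** Section 2.1 says that "the most important risk factors for wound complications in transplantation are immunosuppression and obesity". For BMI above versus below 30 it reports a "significantly higher risk of wound infection (RR = 3.13, CI, 2.08–4.71; P <0.001") and of "wound dehiscence (RR 4.85, CI, 3.25–7.25; P <0.001"). Section 4.6 makes infection, dehiscence and fluid collection within 30 days the primary outcome.
- **Randomisation.** Section 5.4: "Randomisation will be stratified by site, with block randomisation by variable block size in a 1:1 ratio". BMI is not a stratification factor.
- **Primary analysis.** Section 9.3 says that the proportion with a wound complication "will be compared between the Prevena and standard dressing groups using a chi-square test without Yates' continuity correction". It promises an absolute risk change and a number needed to treat.
- **Baseline differences.** Section 9.3 compares the arms' baseline characteristics with t-tests and chi-square tests, but attaches no action to the result.
- **The only regression.** Section 9.3 has a secondary logistic model that searches for risk factors by stepwise selection. It is not specified as an adjusted treatment estimate, and nothing ensures that BMI stays in it.
- **Interim look.** Section 9.4 sets p = 0.001 for the primary outcome at one year.

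**The concern.** When a baseline variable predicts the outcome strongly, leaving it out of the analysis has two costs. The spread in risk that it explains stays in the error, so the treatment effect is estimated less precisely than the same patients allow. And if the arms differ in that variable by chance, the unadjusted difference carries the imbalance with it.

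Here the predictor is identified in the protocol's own background, yet neither the randomisation nor the primary analysis uses it. The baseline tests could reveal an imbalance, but no response to one is written down. An adjusted analysis added after the data are seen would be post hoc and open to challenge, whichever way it moved the result.

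**Working it through.** **Inputs from the documents.** Control rate 15%, Prevena rate 7%, two-sided alpha 0.05, power 80%, 239 per group raised to 250 (9.1); BMI risk ratios 3.13 and 4.85 (2.1).

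**Assumed, because the documents do not give it.** The share f of recipients with BMI >30: 15%, 25% and 35%. The overall rates are held at 15% and 7%, the treatment risk ratio is the same in both BMI groups, and BMI is treated as a two-group variable.

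**Step 1: reproduce the plan.** The formula in 9.1 gives N = {1.96·√(2·0.11·0.89) + 0.84·√(0.15·0.85 + 0.07·0.93)}² / 0.08² = 239 per group, which agrees with the plan. At 250 per arm the same formula gives 81.8% power.

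**Step 2: precision.** With BMI risk ratio R, the low-BMI risk in an arm with overall rate p is p/(1 − f + fR), and the high-BMI risk is R times that. Write d₀ and d₁ for the high-minus-low difference in the control and Prevena arms.

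- Unadjusted variance × n: 0.15·0.85 + 0.07·0.93 = 0.1926
- Adjusted variance × n: 0.1926 − f(1−f)(d₀² + d₁²) + f(1−f)(d₀ − d₁)²/2

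The last term allows for the risk difference varying between BMI groups.

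Example with f = 0.25 and R = 3.13. Control risks are 0.15/1.5325 = 9.8% and 30.6%; Prevena risks are 0.07/1.5325 = 4.6% and 14.3%. So d₀ = 0.2085 and d₁ = 0.0973. Adjusted variance × n = 0.1926 − 0.0099 + 0.0012 = 0.1838, a fall of 4.6%. Effective size is 250 × 0.1926/0.1838 ≈ 262 per arm, or 12 extra.

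| BMI risk ratio in the composite | Variance reduction (f = 15-35%) | Worth, patients per arm | Power at 250 per arm |
|---|---|---|---|
| 3.13 (infection) | 4.2-4.6% | 11-12 | about 83.4% |
| 4.85 (dehiscence) | 7.7-9.5% | 21-26 | about 85% |
| 2 (assumed dilution) | 1.2-1.6% | 3-4 | about 82.2-82.4% |

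For scale, the plan's whole allowance for loss to follow-up is 250 − 239 = 11 per arm.

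**Step 3: chance imbalance.** The between-arm difference in the BMI >30 share has SD √(2f(1−f)/250), which is 3.2 to 4.3 percentage points. The chance that it exceeds 5 points is 2{1 − Φ(0.05/SD)}: 12%, 20% and 24% for f = 15%, 25% and 35%. For more than 10 points it is 0.2-1.9%. The expected shift in the unadjusted risk difference is the imbalance times (d₀ + d₁)/2. For 5 points that is 0.7-1.3 percentage points, against a planned effect of 8 points and a standard error of √(0.1926/250) = 2.8 points.

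**Step 4: simulation.** 200,000 trials per scenario at 250 per arm compared the plain chi-square with a Cochran-Mantel-Haenszel test stratified by BMI.

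| | Plain chi-square | BMI-stratified test |
|---|---|---|
| Type I error, all trials | 5.0% | 5.0% |
| Type I error, imbalance >5 points, ratio 3.13 | 6.4-7.1% | 4.9-5.4% |
| Type I error, imbalance >5 points, ratio 4.85 | 7.5-9.7% | about 5.1% |
| Power, ratio 3.13 | about 82.5% | about 84% |
| Power, ratio 4.85 | about 82.5% | 85-86% |

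**The case against.** The strongest reply is that nothing here is an error. An unadjusted chi-square in a randomised trial is valid, the simulation confirms 5.0% type I error overall, and 250 per arm already exceeds the 80% power target. That stands. The point is an improvement in efficiency and robustness, not a flaw that invalidates the trial.

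A second reply is that the two ratios belong to infection and dehiscence, while the primary outcome also counts fluid collections, for which the documents give no BMI ratio. That stands too, and it is why the working includes a diluted ratio of 2, at which the gain almost disappears.

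A third is that adjustment moves the headline away from the test on which the sample size was built. This is a real cost, met by keeping that test as supportive.

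Three stronger readings are tempting, and the documents do not support them:

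- *Open entry is the fault.* It is not. Broad recruitment is a legitimate choice, and the gap is in the analysis.
- *Section 9.1 assumes its effect in high-BMI patients, which conflicts with all-comer entry.* The phrase there is "in high risk population", attached to lower abdominal and groin wounds with the incision that this trial records. Section 2.1 also lists immunosuppression as a leading risk, so the phrase can equally mean transplant recipients as a whole. No conflict is established.
- *A treatment-by-BMI estimate would show whether the result applies to both BMI groups.* It would not. Under the two published ratios the high-BMI Prevena group has only about 6-13 events. The 95% interval for the ratio of odds ratios then spans a factor of about 3.4-3.8 either way, and power for a twofold interaction is about 18-20%.

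**Conclusion.** The point holds as a modest, inexpensive improvement to section 9.3. The plan leaves out of its primary analysis a predictor that its own background calls leading, and it states no response to a chance imbalance in that predictor. Depending on the unknown BMI ratio for the composite, adjustment is worth from about 3-4 to 21-26 patients per arm, and power rises from 81.8% to between about 82% and 85%. An imbalance above 5 points would occur in about one trial in eight to one in four.

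These sizes rest on the assumed 15-35% share with BMI >30, a two-group BMI split, a common treatment risk ratio, and carrying the infection or dehiscence ratio over to the composite. They do not include any gain from adjusting for site. A reader might infer that the planned test is biased or that the trial's error rate is inflated. Neither follows, because the excess error arises only within the subset of trials that happen to be imbalanced.

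**What to change.** Leave the entry criteria and the randomisation as they are. In section 9.3, pre-specify that:

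1. The primary treatment effect comes from a logistic model with treatment, site and continuous baseline BMI, standardised over the trial population to give the absolute risk difference that 9.3 already promises, with its confidence interval. Site belongs in the model because it is the stratification factor, and 9.1 expects site rates from 5-10% to 18-25%.
2. The unadjusted chi-square is reported as a supportive analysis.
3. Any estimate by BMI group is exploratory.

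In section 9.4, state whether the p = 0.001 interim boundary applies to the adjusted analysis or to the chi-square.

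The cost is a few sentences in the plan and a few lines of analysis code, with no extra patients or visits. The downside is that the headline estimate becomes model-based rather than read from a 2×2 table. The change assumes that BMI is among the baseline data. Section 4.2 records demographics and comorbidities, but the variable list in Appendix C was not in the text available for review, so this should be confirmed.

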5.2.2 Pre-Operative Exclusion Criteria

The participant:

1. has a known allergy or hypersensitivity to silver, or drape materials that contain acrylic adhesives.
2. Is not suitable for closure of the surgical wound, and as such the wound must be left open or an open NPWT device is required.
3. Is not willing to comply with the study procedures.

5.2.3 Intra-Operative Exclusion Criteria

The participant:

1. Has an unforeseen intraoperative event mandating additional management including a planned re-exploration.
2. Has obvious intraoperative contamination of the surgical site.
3. Has a wound with suspected ischaemia in the incision area, or inadequate haemostasis.
4. Requires drains that cannot be covered by the Prevena dressing.

5.3 Informed Consent Process

Informed consent should be obtained in accordance with the applicable regulations, and current versions of Declaration of Helsinki, ICH-GCP and ISO 14155. If a patient might be eligible for the study, a study investigator may approach them to obtain the written informed consent. During the consent process, the background of the proposed study including the benefits and risks of study participation should be explained in detail to the patient.

It has to be emphasized that a patient's participation in the trial is voluntary and that the patient may refuse to participate or withdraw from the trial, at any time, without penalty or loss of benefits to which the patient is otherwise entitled. The patient must be given ample time to read the patient information and to address questions before signing the consent form. Study information and a copy of the Ethics Committee approved consent form will be signed (by the Investigator and participant). Patients are considered provisionally enrolled in the study once they have signed the Consent Form. Enrolled participants should be treated within 30 days from the day of Consent. If the index procedure is not performed within 30 days of the provisional enrolment the participant must be re-screened and written informed consent re-obtained.

5.4 Enrolment and Randomisation Procedures

All patients presenting for a renal transplant over a 24 month period at one of the participating sites will be eligible for enrolment in this study. Patients who sign the Participant Information Sheet and Consent Form (PISCF) and fulfil all inclusion and exclusion criteria, as well as compliance with contraindications listed in the Prevena IFU, will be considered eligible for study participation. Participants may recruited at any point prior to surgery once surgery is confirmed, ideally at the time of admission to hospital for the procedure, or if this is not possible, at the time consent is obtained for the surgery. A unique study identification number is then assigned to enrolled participant by the study investigators.

Participants who signed the PISCF but do not fulfil all inclusion and exclusion criteria, IFU related indications and contraindications, hospital standard of care tests, or who withdraw informed

consent prior to the procedure are screen failures. They will be documented on the screening and enrolment log with the screening failure reason. For the purposes of analysis, an Intention to Treat (ITT) sample will be based on all enrolled subjects, and a secondary as per-protocol analysis will be based on all patients who have the intervention of having a dressing placed on the closed incision following renal transplant.

Patient registration will occur prior to surgery on an online research database (REDCap; Vanderbilt University, Nashville, USA) hosted at Royal North Shore Hospital (19). Randomisation via REDCap will occur when the patient fulfils all intra-operative exclusion criteria and after commencement of skin closure (defined as closure to the muscle, subcutaneous tissue and skin). Randomisation will be stratified by site, with block randomisation by variable block size in a 1:1 ratio. , The surgical team, clinical staff, and patient will not be blinded to the intervention status.

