Study Procedures	Participants will be randomised to either a Prevena (intervention arm) or standard dressing (control arm) is placed on the closed incision after renal transplantation. Monitoring will occur daily during hospitalization and up to 30 days postoperatively to review any wound complications, with subsequent assessment at 90 days.
Statistical Procedures and Analysis Plan:	Statistical analysis will be pre-specified and conducted according to both principles of intention of treat and per-protocol analysis, using SPSS version 20 (IBM, Armonk, NY, USA). The Intention to Treat (ITT) sample will be based on all enrolled subjects, and the per-protocol analysis will be based on all patients who have a dressing placed on the closed incision following renal transplant. Each incision will be randomized to the Prevena or standard dressing group. In the case that a patient requires bilateral incisions, both incisions will be allocated to the same treatment arm and counted as a single incision. Baseline characteristics of the two groups will be recorded and compared using Student's t-test and chi-square test for continuous and discrete data respectively. The primary outcome, the proportion of wound complications, will be compared between the Prevena and standard dressing groups using a chi-square test without Yates' continuity correction with a two-sided alpha of 0.05 at the final analysis using the Peto approach to preserve the overall

	
significance level of 0.05 (23). Patients lost to follow-up will be used in an intention-to-treat analysis with last observation carried forward
 
The secondary outcome of identification of risk factors for wound complications will be assessed by multiple logistic regression of collected variables to assess their odds ratio.

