4.2 Study Design

Ethics approval will be obtained from SLHD-RPA by the Lead site at RNSH. All sites will require Governance approval prior to study commencement. Enrolled participants in this study will present for renal transplantation at a participating study site, having received routine planning and workup for the operation which will include education regarding the trial, and providing informed consent at the time of admission for the operation. Study investigators will register the patient in an online database (REDCap Database Vanderbilt University) controlled by the study investigators, which will randomly allocate the patient to a treatment arm, to be revealed after transplantation and during the closure procedure (closure defined as closure to the muscle, subcutaneous tissue or skin). Patient data variables including demographic data, medical comorbidities and pathology results will be recorded from the patient electronic medical record (see appendix). Details of the donor kidney will be also be recorded, including donor demographics, anatomical characteristics, ischaemic time, and time of retrieval.

The patient will be prepared for surgery as per site specific protocols; variables to be recorded include peri operative antibiotic administration and skin preparation (application of an antiseptic agent such as chlorhexidine or iodine, or iodine impregnated drapes). Each surgeon will proceed with the procedure of renal transplantation as per operator preference. Operative details to be recorded include site and side of incision (Rutherford-Morrisson), warm ischaemic time, time of reperfusion, operation duration, estimated blood loss, length of incision, and method (materials; eg. sutures, staples) of closure in layers (muscle, subcutaneous tissue and skin). Drain presence and placement is also recorded. Bilateral renal transplants and bilateral incisions will be counted as one incision and will allocated to the same treatment arm as one entity.

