5.6.2 Handling of withdrawals

[figure not shown]
All participants withdrawn will ideally complete all study visits including Day 30 follow-up if able, as per routine clinical practice. Withdrawn patients will be included in an intention to treat analysis.

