9.2 Population to be analysed

Every patient presenting for renal transplant that meets the criteria for inclusion and exclusion will be included for intention to treat analysis. Secondary analysis as per protocol will also be performed.

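### The ITT set is defined in two different ways and never as all randomised patients; section 9.2 read literally would remove a randomised patient later found ineligible

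*Combined protocol and SAP*

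**What the plan says.** Three places define the intention-to-treat set.

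- Synopsis, statistical procedures: "The Intention to Treat (ITT) sample will be based on all enrolled subjects".
- Section 5.4: "an Intention to Treat (ITT) sample will be based on all enrolled subjects".
- Section 9.2: "Every patient presenting for renal transplant that meets the criteria for inclusion and exclusion will be included for intention to treat analysis".

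The timing comes from other sections. Section 5.3: "Patients are considered provisionally enrolled in the study once they have signed the Consent Form". Section 5.4 places registration before surgery and then states: "Randomisation via REDCap will occur when the patient fulfils all intra-operative exclusion criteria and after commencement of skin closure". Section 4.2 describes registration in a database "which will randomly allocate the patient to a treatment arm, to be revealed after transplantation and during the closure procedure".

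On patients who leave, section 5.4 classes as screen failures "Participants who signed the PISCF but do not fulfil all inclusion and exclusion criteria", and section 5.6.2 states: "Withdrawn patients will be included in an intention to treat analysis".

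**The concern.** An intention-to-treat comparison protects against selection only if its denominator is fixed at randomisation. Here enrolment starts at consent, four intra-operative exclusions follow (5.2.3), and randomisation comes during closure. A set defined by enrolment begins too early. A set defined by eligibility can be revised afterwards, because a criterion may be found unmet once the arm is known.

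The second problem matters more. Sections 5.4 and 5.5 state that the surgical team and treating staff are not blinded. Several criteria concern whether the patient suits the device: an incision that Prevena is likely to cover (5.2.1 item 4), allergy to silver or acrylic adhesive (5.2.2 item 1), drains the dressing cannot cover (5.2.3 item 4) and the IFU contraindications (5.4). A late discovery of this kind is more likely to come to light in a patient wearing the device than in one with a standard dressing. Removal on that ground could therefore be unblinded and unequal between arms, in the primary analysis.

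**Working it through.** **1. Patient types against each rule.**

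| Patient | Synopsis and 5.4 (enrolled) | 9.2 (meets criteria) | 5.6.2 (withdrawn) |
|---|---|---|---|
| Consented, excluded during surgery | In if consent counts as enrolment; out if a screen failure is not enrolled | Out | Not addressed |
| Eligible, never consented | Out | In, read literally | Not addressed |
| Randomised, later found ineligible, not withdrawn | In | Out | Not addressed |
| Randomised, withdrawn for an IFU contraindication (5.6.1) | In | Arguably out | In |
| Randomised, Prevena removed early | In | In | Stays in its arm under 4.2 |

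The third and fourth rows affect the primary comparison, because those patients have an arm. The plan gives no rule of precedence. The first row matters only if those patients already hold an allocation, which leads to step 2.

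**2. Time of allocation.** Section 5.4 generates the allocation after the intra-operative check. Section 4.2 can be read as the database allocating at registration, with the arm disclosed at closure. On that reading every intra-operative exclusion is a post-randomisation exclusion. The sections need to be reconciled.

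**3. The plan's sample size.** Inputs from 9.1: 15% v 7%, two-sided alpha 0.05, power 80%, 1:1, no continuity correction. With the plan's rounded z values:

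N = {1.96 × √(0.11 × 0.89 × 2) + 0.84 × √(0.15 × 0.85 + 0.07 × 0.93)}² / 0.08² = (0.8673 + 0.3686)² / 0.0064 = 238.7, so 239 per group.

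This reproduces the plan. Power is 80.0% at 239 and 81.8% at 250 per arm. Nothing in this point changes those figures.

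**4. Illustrations under assumed rates.** The documents give no intra-operative exclusion rate; 5%, 10% and 15% are assumed.

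- If the 500 were counted at enrolment and excluded patients had no arm, 475, 450 or 425 would be randomised, with power 79.8%, 77.6% or 75.2%. The allowance of 500 − 478 = 22 is used up at 22/500 = 4.4%.
- If allocation were at registration, and excluded patients were analysed at 15% in both arms, the Prevena rate would be (1 − f) × 7% + f × 15% = 7.4%, 7.8% or 8.2%, with power at 250 per arm of 77.0%, 71.8% or 66.1%.

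**5. How little selection is needed near the threshold.** Invented counts, chi-square without correction: 37/250 v 23/250 gives p = 0.054. Removing one Prevena patient who had an event (37/250 v 22/249) gives p = 0.039. This shows sensitivity to a single eligibility decision; it does not predict one.

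**The case against.** The strongest reply is that, read together, the sections come close to the conventional set. Consent gives only provisional enrolment (5.3). The intra-operative exclusions sit under the eligibility heading, so a patient excluded during surgery is naturally a screen failure under 5.4. Section 5.4, the dedicated randomisation section, randomises only those who pass. Early device removal does not change the arm (4.2). A randomised patient with an IFU contraindication may be withdrawn with documented reasons (5.6.1) and then stays in the analysis (5.6.2). Section 4.3 already expresses the target as about 250 allocated to each arm.

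Most of this stands, and it disposes of three stronger readings that a reader might infer.

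- *That patients without an arm would enter the primary test.* They cannot enter a two-arm chi-square, and the screen-failure rule points to leaving them out. What remains is that the plan never says screen failures lie outside the enrolled set.
- *That power falls to between 66% and 80%.* The lower figures need the adverse reading of 4.2, disregard of screen-failure status, an unsourced exclusion rate and an assumed event rate. The others need the 500 to be counted at enrolment, which 4.3 does not support.
- *That the plan directs removal from the Prevena arm.* It does not. Section 9.2 states who is included, and 5.6.2 protects withdrawn patients.

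The reply does not cover a randomised patient found ineligible and not formally withdrawn, or say whether 9.2 or 5.6.2 governs when both apply. Nor does it remove the mismatch between 4.2 and 5.4.

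**Conclusion.** The point holds as a defect in the definition of the primary analysis set. The plan gives two non-equivalent rules, neither is all randomised patients, and 9.2 read literally conflicts with 5.6.2. The exposure is limited: mainly randomised patients found ineligible but not formally withdrawn, plus intra-operative exclusions if allocation is generated at registration.

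The harm at issue is possible selection after randomisation by people who know the arm. Its size cannot be estimated from the documents. That it would fall more on the Prevena arm is an inference from the device-related criteria, not something the plan states. The power figures in the working are illustrations under assumed rates and are not evidence of harm. No stated figure is wrong, and 239 (250 after rounding up) per arm stands.

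**What to change.** - In the synopsis, 5.4 and 9.2, use one definition: *all randomised patients, analysed in the arm allocated, whether or not later found ineligible, withdrawn or not given the allocated dressing*.
- In 4.2, separate registration from allocation and match 5.4, so that the allocation is generated only after the intra-operative exclusions have been recorded as passed. Check that the REDCap randomisation step is set up this way.
- State that consented patients who are not randomised, including intra-operative exclusions, appear in the flow diagram only, and that the 500 counts randomised patients, in line with 4.3.

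The cost is wording in four places and possibly one database setting. No patients, visits or assessments are added, and the sample size calculation is unchanged.
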